2.5.2 Prior, concomitant and post therapies

2.5.2.1 Prior anti-cancer therapy

The number and percentage of participants who received any prior anti-neoplastic (ANP) medications, prior anti-neoplastic radiotherapy or prior anti-neoplastic surgery will be summarized using the FAS.

Prior anti-neoplastic medications will be summarized by therapy type (e.g., chemotherapy, immunotherapy, etc.), setting (e.g., adjuvant, neo-adjuvant), number of prior regimens of anticancer medications, therapy type and setting at last medication (based on the last start date of all prior regimen components). The medication therapy type of any combination therapy will be counted in each category. For example, a participant receiving a combination of chemotherapy and immunotherapy will be counted under “chemotherapy” and “immunotherapy”. Prior antineoplastic medications will also be summarized by ATC class, and preferred term.

Anti-neoplastic medications will be coded using the World Health Organization (WHO) Drug Dictionary (WHO-DD). Details regarding the WHO-DD version will be included in the footnotes of the tables and listings.

For radiotherapy, time since last radiotherapy, locations and setting of last therapy will be summarized.

For prior surgery, time since last surgery, procedure and residual disease of last therapy will be summarized.

Separate listings will be produced for prior anti-neoplastic medications, radiotherapy, and surgery.

2.5.2.2 Post-treatment anti-cancer therapy

Anti-neoplastic therapies since discontinuation of study treatment will be listed and summarized by therapy type and number of post-treatment therapies received using the FAS.

Anti-neoplastic medications initiated after discontinuation of study treatment will be listed and summarized by Anatomical Therapeutic Chemical (ATC) class, preferred term.

Anti-neoplastic radiotherapy as well as anti-neoplastic surgery since discontinuation of study treatment will be summarized and listed.

2.5.2.3 Concomitant therapy

Concomitant therapy will be summarized for all interventions (therapeutic treatments, surgeries and procedures) other than the study treatment administered to a participant coinciding with the on-treatment period.

Concomitant therapy includes medications (other than the study treatment) starting on or after the start date of study treatment or medications starting prior to the start date of study treatment and continuing after the start date of study treatment.

Concomitant medications will be coded using the WHO Drug Reference Listing (WHO DRL) dictionary that employs the WHO ATC classification system and summarized by lowest ATC class and preferred term. These summaries will include

- Medications starting on or after the start date of study treatment but no later than 30 days after the last date of administration of study treatment and
- Medications starting prior to the start date of study treatment and continuing after the start date of study treatment (in the on-treatment period)

In addition, surgical and medical procedures will be coded using MedDRA and summarized by SOC and preferred term.

All concomitant therapies will be listed. Any concomitant therapies starting and ending prior to the start date of study treatment or starting more than 30 days after the last date of study treatment will be flagged in the listing.

The safety set will be used for all concomitant therapy tables and listings.

2.6 Analysis supporting primary objective(s)

The primary objective of the study is to assess the antitumor activity of JDQ443 single-agent as first-line treatment for participants with locally advanced or metastatic NSCLC whose tumors harbor a KRAS G12C mutation and a PD-L1 expression < 1%, regardless of STK11 mutation status (cohort A). The primary analysis of the primary and key secondary endpoint will be conducted when participants in the respective cohort who are still receiving study treatment will have completed at least 4 tumor assessments or discontinued earlier (approximately 24 weeks), provided that cohort A was not declared futile at the interim analysis.

Depending on the enrollment and follow-up of the participants in the two cohorts, the analysis of the primary and key secondary endpoint can also be analyzed at the same time.

The analysis will be based on the FAS and will include all participant data observed up to the cut-off date.

2.6.1 Primary endpoint(s)

The primary clinical question of interest and the primary estimand are defined in [Section 1.2.1](#).

The primary endpoint is ORR, defined as the proportion of participants with a confirmed CR/PR as BOR. BOR is defined as the best response recorded from the start of the treatment until disease progression per RECIST 1.1 by BIRC. Complete and partial responses must be

confirmed by repeat assessments that should be performed not less than 4 weeks after the criteria for response were first met. Responses documented after the use of any new anti-neoplastic therapy will be considered as non-response (with the exception of protocol-allowed radiotherapy).

The BOR will be determined from response assessments undertaken while on treatment. In addition, only tumor assessments performed before the start of any further anti-neoplastic therapy (with the exception of protocol-allowed radiotherapy) will be considered in the assessment of BOR.

BOR for each participant is determined from the sequence of overall (lesion) responses according to the following rules:

- CR = at least two determinations of CR at least 4 weeks apart before progression;
- PR = at least two determinations of PR or better at least 4 weeks apart before progression (and not qualifying for a CR);
- SD = at least one SD assessment (or better) > 5 weeks after start of treatment (and not qualifying for CR or PR);
- Non-CR/non-PD* = at least one Non-CR/non-PD assessment > 5 weeks after start of treatment (and not qualifying for CR);
- PD = progression ≤ 13 weeks after start of treatment (and not qualifying for CR, PR or SD);
- NE = all other cases (i.e., not qualifying for confirmed CR or PR and without SD after more than 5 weeks or early progression within the first 13 weeks).

* For participants with only non-measurable disease present at baseline. A non-CR/non-PD response is considered equivalent to an SD response for the ORR determination and participants will be considered “non-responders”.

Participants with ‘NE’ BOR will be summarized by reason for having NE status. The following reasons will be used:

- No valid post-baseline assessment
- All post-baseline assessments have overall lesion response NE
- New anti-neoplastic therapy started before first post-baseline assessment
- SD too early (≤ 5 weeks after start of treatment)
- PD too late (> 13 weeks after start of treatment)

Note 1: An SD is considered as “SD too early” if the SD is documented within the first 5 weeks after the start of treatment date.

Note 2: A PD is considered as “PD too late” if the first documentation of PD is recorded more than 13 weeks after the start of treatment date with no qualifying CR, PR or SD in between.

Note 3: Special (and rare) cases where BOR is “NE” due to both too early SD and too late PD will be classified as “SD too early”.

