3.1 Primary estimands

The estimand is the precise description of the treatment effect and reflects strategies to address events occurring during trial conduct which could impact the interpretation of the trial results (e.g., premature discontinuation of treatment).

The primary clinical question of interest is: What is the effect of JDQ443 monotherapy in inducing radiological response per RECIST 1.1 assessed by BIRC when administered as first-

line treatment for participants with locally advanced or metastatic NSCLC whose tumors harbor a KRAS G12C mutation and a PD-L1 expression < 1% (cohort A), regardless of study treatment discontinuation and any unforeseen events resulting from a public health emergency?

The justification for the primary estimand is that it will capture the treatment effect irrespective of study treatment discontinuation but avoids the confounding effect of any new anti-cancer therapy that is not a part of the originally assigned treatment.

The primary estimand is described by the following attributes:

- 1. Population: Adult participants with locally advanced or metastatic NSCLC without previous systemic treatment for metastatic disease whose tumors harbor a KRAS G12C mutation and a PD-L1 expression < 1%, irrespective of STK11 mutation status (cohort A).
- 2. Primary variable: BOR defined as the best response recorded from the start of the treatment until disease progression per RECIST 1.1 by BIRC, with responses documented after the use of any new anti-neoplastic therapy considered as non-response.
- 3. Treatment of interest: All participants enrolled in this study will be treated with JDQ443 a selective and irreversible KRAS G12C inhibitor administered p.o. 200 mg twice a day continuously.
- 4. Handling of remaining intercurrent events:
 - Treatment discontinuation for any reason: Tumor assessment data collected irrespective of treatment discontinuation will be included to derive BOR (treatment policy strategy).
 - Any public health emergency as declared by local or regional authorities, i.e., pandemic, epidemic or natural disaster: tumor assessment data collected irrespective of such unforeseen events will be considered for the BOR (treatment policy strategy).
 - New anti-cancer therapy: If any new anti-neoplastic therapy is initiated, responses
 documented after the use of new anti-neoplastic therapy will be considered as nonresponse (composite strategy).

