- If central radiology does not confirm progressive disease, the study site will be informed. As long as it is clinically acceptable, every effort should be made to continue the participant on study treatment until progressive disease is confirmed by BIRC or for at least one subsequent radiological timepoint.

Time points without locally determined progression

All imaging time points without locally determined progression will be read on an ongoing, non-expedited basis as detailed in the imaging manual to be provided by the designated imaging CRO and independent review charter. Results of these readings will not be communicated to the sites.

Treatment beyond disease progression

Following determination of disease progression, if the Investigator believes the participant treated with JDQ443 may derive benefit from continuing study treatment, the participant will be permitted to continue treatment beyond initial disease progression as per RECIST 1.1 by BIRC. Please see Section 6.1.4.1 for additional information.

Efficacy follow-up imaging assessments

For participants who discontinue treatment for reasons other than initial disease progression as per RECIST 1.1, tumor assessments must continue to be performed as outlined in Table 1-3 regardless if participants start on new antineoplastic therapy before documented disease progression. Please refer to Section 8.4 for additional information.

As per Section 4.5, during a Public Health emergency as declared by Local or Regional authorities i.e., pandemic, epidemic or natural disaster, that limits or prevents on-site study visits, the collection of images (e.g., change of imaging center or imaging frequency) may be modified by Novartis and will be communicated to the Investigator.

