10.8.3.1 Best overall response

The best overall response is the best response recorded from the start of the treatment until disease progression/recurrence (taking as reference for PD the smallest measurements recorded since the treatment started). In general, the patient's best response assignment will depend on the achievement of both measurement and confirmation criteria.

The best overall response will usually be determined from response assessments undertaken while on treatment. However, if any assessments occur after treatment withdrawal the protocol should specifically describe if these will be included in the determination of best overall response and/or whether these additional assessments will be required for sensitivity or supportive analyses. As a default, any assessments taken more than 30 days after the last dose of study treatment will not be included in the best overall response derivation. If any alternative cancer therapy is taken while on study any subsequent assessments would ordinarily be excluded from the best overall response determination. If response assessments taken after withdrawal from study treatment and/or alternative therapy are to be included in the main endpoint determination, then this should be described and justified in the protocol.

Where a study requires confirmation of response (PR or CR), changes in tumor measurements must be confirmed by repeat assessments that should be performed not less than 4 weeks after the criteria for response are first met.

Longer intervals may also be appropriate. However, this must be clearly stated in the protocol. The main goal of confirmation of objective response is to avoid overestimating the response rate observed. In cases where confirmation of response is not feasible, it should be made clear when reporting the outcome of such studies that the responses are not confirmed.

- For non-randomized trials where response is the primary endpoint, confirmation is needed
- For trials intended to support accelerated approval, confirmation is needed
- For all other trials, confirmation of response may be considered optional

The best overall response for each patient is determined from the sequence of overall (lesion) responses according to the following rules:

- CR = at least two determinations of CR at least 4 weeks apart before progression where confirmation required or one determination of CR prior to progression where confirmation not required

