2.1.3.8 On-treatment assessment/event and observation periods

For adverse event reporting the overall observation period will be divided into three mutually exclusive segments:

1. ***pre-treatment period:*** from day of participants informed consent to the day before first administration of study treatment

2. **on-treatment period:** from date of first administration of study treatment to 30 days after date of last actual administration of study treatment (including start and stop date)
3. **post-treatment period:** starting at day 31 after last administration of study treatment.

Safety summaries (tables, figures) and summaries of on-treatment deaths include only data from the on-treatment period with the exception of baseline data which will also be summarized where appropriate (e.g. change from baseline summaries). In addition, all deaths which occurred during the study (i.e. during the on-treatment, and post-treatment periods) will be summarized.

An on-treatment adverse event (or treatment-emergent AE) is defined as any adverse event reported in the on-treatment period.

An on-treatment assessment is defined as any assessment performed during the on-treatment period.

In case at the time of the analysis, the date of last administration of study treatment is missing, on-treatment adverse events/assessments include any adverse event/assessment recorded in the database and which occur after the start date of the study treatment.

Data listings will include all assessments/events, flagging those which were collected during the pre-treatment and post-treatment period.

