2.6.3 Handling of intercurrent events

The primary analysis will account for different intercurrent events as follows:

1. Discontinuation of study treatment: Tumor assessment data collected after discontinuation of study treatment for any reason will be included to derive BOR (treatment policy strategy).
2. Start of a new anti-neoplastic therapy: If any new anti-neoplastic therapy is initiated, responses documented after the use of new anti-neoplastic therapy will be considered as non-response (composite strategy). Protocol-allowed radiotherapy is exempted.
3. Any public health emergency as declared by local or regional authorities, i.e., pandemic, epidemic or natural disaster: Tumor assessment data collected irrespective of such unforeseen events will be considered for the BOR (treatment policy strategy).

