2.7.1 Key secondary endpoints

The key secondary endpoints are ORR in cohort B as well as duration of response in both cohorts (A and B).

ORR by BIRC for cohort B

ORR per RECIST 1.1 by BIRC in cohort B is defined in the same way as specified in [Section 2.6.1](#).

DOT by BIRC for cohort A and cohort B

Duration of response is defined as the duration of time between the date of first documented response (PR or CR) and the date of the first documented radiological progression or death due to any cause. DOT will be evaluated based on the BIRC assessment.

DOT only applies to participants whose best overall response is CR or PR based on tumor response data per BIRC assessment. If a participant has not had an event, DOT will be censored at the date of the last adequate tumor assessment using the censoring rules described in [Table 2-5](#). Participants who never achieved a BOR of CR or PR will be excluded from the analysis.

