2.7.3 Handling of intercurrent events

ORR by BIRC for cohort B

The analysis will account for different intercurrent events as follows:

1. Treatment discontinuation for any reason: Tumor assessment data collected irrespective of treatment discontinuation will be included to derive BOR (treatment policy strategy).
2. Start of a new anti-neoplastic therapy: If any new anti-neoplastic therapy is initiated, responses documented after the use of new anti-neoplastic therapy will be considered as non-response (composite strategy). Protocol-allowed radiotherapy is exempted.

3. Any public health emergency as declared by local or regional authorities, i.e., pandemic, epidemic or natural disaster: tumor assessment data collected irrespective of such unforeseen events will be considered for the BOR (treatment policy strategy).

DOR by BIRC for cohort A and cohort B

The analysis will account for different intercurrent events as follows:

1. Treatment discontinuation for any reason: Tumor assessment data collected irrespective of treatment discontinuation will be included to derive DOR (treatment policy strategy).
2. Start of a new anti-neoplastic therapy: If any new anti-neoplastic therapy (with the exception of protocol-allowed radiotherapy) is initiated, progression or death occurring after the use of new anti-neoplastic therapy will not be considered and the DOR will be censored.
3. Any public health emergency as declared by local or regional authorities, i.e., pandemic, epidemic or natural disaster: tumor assessment data collected irrespective of such unforeseen events will be considered for the DOR (treatment policy strategy).

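### The SAP defines best overall response, and so the primary ORR, in two incompatible ways: on-treatment scans only (2.6.1) and scans regardless of treatment discontinuation (2.6.3 and the estimand)

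*SAP*

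**What the plan says.** **The endpoint definition (SAP 2.6.1).** After defining ORR from a confirmed CR or PR, the section says: "The BOR will be determined from response assessments undertaken while on treatment". The next sentence adds, as a further condition, that only scans before new anti-neoplastic therapy count. The on-treatment limit is therefore a restriction of its own and not shorthand for the new-therapy cut.

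**The intercurrent-event rule (SAP 2.6.3).** For the same endpoint: "Tumor assessment data collected after discontinuation of study treatment for any reason will be included to derive BOR". This is labelled treatment policy. SAP 1.2.1, Protocol 3.1 and Protocol 9.3.3 say the same. Protocol 9.3.1 defines the endpoint with no on-treatment limit.

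**Cohort B (key secondary).** SAP 2.7.1 says "ORR per RECIST 1.1 by BIRC in cohort B is defined in the same way as specified in" Section 2.6.1, which imports the on-treatment sentence. SAP 2.7.3 then restates treatment policy for cohort B.

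**The generic default.** Protocol Appendix 8, 10.8.3.1, says: "The best overall response will usually be determined from response assessments undertaken while on treatment". By default it leaves out scans more than 30 days after the last dose, and it asks the protocol to state and justify any departure.

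**Data collection.** For participants who stop drug for reasons other than progression, Protocol 8.4.1 says "tumor assessments must continue to be performed as outlined in Table 1-3".

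**The concern.** A programmer who derives best overall response from 2.6.1 drops post-discontinuation scans. A programmer who follows 2.6.3 keeps them. Both have followed the SAP, and they can report different primary ORRs.

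The conflict spreads to everything built on best overall response: cohort B ORR, disease control rate, the investigator-assessed supplementary estimand and the set of responders for duration of response. Duration of response itself follows treatment policy (SAP 2.7.3). Under 2.6.1, responders would therefore be chosen from one set of scans and their response timed on another.

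The estimand was chosen to capture the effect irrespective of treatment discontinuation. The on-treatment rule answers a different question and discards scans the protocol requires. If the conflict is found only after the data have been seen, the choice between definitions becomes post hoc.

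**Working it through.** **1. The passages side by side**

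| Source | Scans after drug stop, before progression and new therapy |
|---|---|
| SAP 2.6.1 | excluded |
| SAP 2.6.3, SAP 1.2.1 | included |
| Protocol 3.1, 9.3.3 | included |
| Protocol 9.3.1 | no on-treatment limit |
| Cohort B: SAP 2.7.1 (via 2.6.1) | excluded |
| Cohort B: SAP 2.7.3 | included |

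**2. Who is classified differently**

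Inputs: scans every 6 weeks ±7 days from C1D1 (Protocol Table 8-1), and confirmation at least 4 weeks after first response (SAP 2.6.1). Take a first PR on study day 43 (week 6), last dose on day D, and a confirming scan on day S, nominally day 85 (week 12). The interval is 85 − 43 = 42 days, so the scan can confirm.

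- If on treatment means last dose plus 30 days, the scan is lost when D < S − 30.
- If it means literally while taking drug, the scan is lost when D < S.

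| Reading | S | Last-dose days that lose the confirmation | Length |
|---|---|---|---|
| last dose + 30 days | 85 | 43–54 | 12 days |
| last dose + 30 days | 78 (earliest in window) | 43–47 | 5 days |
| last dose + 30 days | 92 (latest in window) | 43–61 | 19 days |
| literal | 85 | 43–84 | 42 days |

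Example: PR on day 43, last dose on day 50, PR again on day 85. The second scan is 85 − 50 = 35 days after the last dose. The participant is a responder under 2.6.3. Under 2.6.1 the only usable scan is one PR more than 5 weeks after start, which gives stable disease and a non-responder. Participants whose first response appears after drug stop are affected in the same way. Responses already confirmed on treatment are not affected.

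**3. What one reclassified responder does**

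The lower limit of the two-sided 95% exact interval is L = the 0.025 quantile of Beta(x, n − x + 1). The rejection rule is L ≥ 35% for cohort A, n = 90 (SAP 2.6.2), and L ≥ 20% for cohort B, n = 30 (SAP 2.7.2).

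| Cohort | x/n | L | CI condition |
|---|---|---|---|
| A | 40/90 | 33.96% | fails |
| A | 41/90 | 35.02% | met |
| B | 11/30 | 19.93% | fails |
| B | 12/30 | 22.66% | met |

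One lost responder changes the CI conclusion only if the count under the estimand sits exactly on the threshold. The binomial probability of that, at assumed true ORRs:

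- P(X = 41 of 90): 8.4% at 45%, 5.9% at 50%.
- P(X = 12 of 30): 14.7% at 40%, 8.1% at 50%.

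These are probabilities of being on the threshold, not of a changed conclusion. A change also requires that a responder is in fact reclassified, and the documents give no rate for that.

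**4. Direction**

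Removing scans can turn a responder into a non-responder but not the reverse. The 2.6.1 rule therefore gives an ORR equal to or below that of the estimand, and type I error is not inflated.

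**The case against.** **The intention is clear.** SAP 2.6.1 opens by pointing to the estimand, four other sections state treatment policy, SAP 2.6 says the analysis uses all data up to the cut-off, and the list of reasons for a not-evaluable response has no category for off-treatment scans. The disputed sentence looks like leftover Appendix 8 text. This is a fair account of how it arose. But the SAP sets no order of precedence, 2.6.1 is where the derivation rules sit, and the sentence is firmer than its source because it drops the qualifier. The not-evaluable list settles little, since the participant in the example would be stable disease.

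**On treatment has a definition.** SAP 2.1.3.8 introduces its periods with "For adverse event reporting the overall observation period will be divided into three mutually exclusive segments", but it stands among the general definitions and also defines an on-treatment assessment as any assessment up to 30 days after the last dose. That makes the 30-day reading the better supported one, although 2.6.1 does not cite it. It narrows the conflict without removing it. The worked example does depend on scan timing: with a last dose on day 50, a week-12 scan on days 78 to 80 would count under both rules.

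**The thresholds are partial.** This stands. They cover the CI condition only. Cohort A's observed-ORR condition is redacted. For cohort B, Protocol 9.4.1.1 asks for an observed ORR above 40%, while 9.2.1 speaks of 40%. If the inequality is strict, 12/30 = 40.0% fails and 13/30 = 43.3% is needed.

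**Conclusion.** The concern holds. The primary endpoint and the key secondary ORR each have two definitions in the same SAP, and the conflict survives the most lenient reading of on treatment. The effect on the estimate is probably small: at nominal scan times it needs drug to stop within a 12-day range after a first response on day 43 (42 days on the literal reading), or a first response off drug, in each case without progression or new therapy. The size cannot be stated further without an assumed share. The correction is nevertheless required, because a primary endpoint should not depend on which section is programmed.

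A separate, minor slip is in SAP Table 2-6 (duration of response and PFS). The row for treatment stopped on claimed clinical progression tells the analyst to disregard new anticancer therapy. The corresponding option in Protocol Table 10-12, row E(1), disregards the clinical progression. As written, the row contradicts the next row of Table 2-6, SAP 2.7.3, SAP 2.8.1.4 and Protocol 9.4.1.2, all of which censor at new therapy.

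**What to change.** In SAP 2.6.1, replace the on-treatment sentence with wording such as: *BOR uses every assessment by the relevant reviewer (BIRC for the primary analysis, investigator for local-review analyses) from first dose up to progression or new anti-neoplastic therapy, whichever is earlier, whether or not study treatment has stopped; protocol-allowed radiotherapy does not count as new therapy.* Cohort B ORR then follows through 2.7.1. A note that the 30-day default in Protocol Appendix 8 does not apply would help but is optional. If an on-treatment response rate is of interest, it can be reported as a labelled supplementary analysis.

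In SAP Table 2-6, change the clinical-progression row so that clinical progression is what is disregarded, as in Protocol Table 10-12, row E(1).

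The cost is SAP wording only. The post-discontinuation scans are already required, and no design, sample-size or data-collection change follows. The change should be made before database lock.
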